12.4 PARTICIPANT AND DATA CONFIDENTIALITY19

CONFIDENTIAL

This material is the property of the NYU School of Medicine and Langone Medical Center. Do not disclose or use except as authorized in writing by the study sponsor

13	DATA HANDLING AND RECORD KEEPING	19
13.1	DATA COLLECTION AND MANAGEMENT RESPONSIBILITIES	19
13.2	STUDY RECORDS RETENTION.....	19
13.3	PROTOCOL DEVIATIONS	19
13.4	PUBLICATION AND DATA SHARING POLICY	20
14	STUDY FINANCES.....	20
14.1	COSTS TO THE PARTICIPANT	20
14.2	PARTICIPANT REIMBURSEMENTS OR PAYMENTS.....	20
15	CONFLICT OF INTEREST POLICY.....	20
16	ATTACHMENTS	21

CONFIDENTIAL

List of Abbreviations

AE	Adverse Event/Adverse Experience
HIPAA	Health Insurance Portability and Accountability Act
ICF	Informed Consent Form
IRB	Institutional Review Board
PI	Principal Investigator
VR	Virtual Reality
PwMS	People with Multiple Sclerosis

CONFIDENTIAL

Protocol Summary

[figure not shown]
Title	Virtual Reality (VR) to improve Quality of Life in Patients diagnosed with Neurological Disorders
Short Title	VR to improve Quality of Life
Brief Summary	Participants with neurological disorders will be recruited to complete sessions of virtual reality (VR) immersion. VR has been shown to have therapeutic benefit in certain patient populations and requires further clinical study to determine the extent to which VR can be used to rehabilitate and reduce symptom burden. This study seeks to pilot newly developed VR methods and collect preliminary data in order to support research grants and inform larger clinical trials. This proposed study will explore the tolerability and preliminary efficacy of Virtual Reality (VR), specifically to determine whether VR can acutely reduce the severity of symptom burden caused by neurological disorders. Additionally, a second group of MS participants with clinically significant pain will be recruited to test the analgesic effects of VR.
Phase	N/A
Objectives	Specific Aim 1: To test the feasibility and tolerability of immersive VR therapy in patients with neurological disorders. Specific Aim 2: To measure the efficacy of a VR program to manage chronic pain for people with multiple sclerosis.
Methodology	Study Group 1: Open-Label Study Group 2: Single blinded, randomized treatment allocation to one of two VR treatment conditions
Endpoint	Completion of up to twelve one-hour sessions of VR alongside study measures taken at the end of the last completed session

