4.1 Description of Study Design

Study Group 1 (Neurological Disorders):

The study is intended as a pilot trial for VR in neurological conditions. An open-label design will be implemented. Once participants are found eligible, they will complete one full session of VR using a headset preconfigured by study personnel. Participants will complete up to twelve sessions of VR therapy that may extend as long as an hour in length. Total number of study visits will be up to the study personnel's discretion. Study personnel will guide VR headset placement and program assignment (i.e., interactive or passive catalogues).

Study Group 2 (Chronic Pain in MS): The study will include an arm for people with MS (PwMS) and chronic pain. We will determine the efficacy of VR for the management of chronic pain in PwMS. Participants in this study group will receive eight treatment sessions over four weeks. Participants will be blinded to the VR treatment catalogue they receive.

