6.1.1 Administration of Device

Participants will be able to complete a maximum of twelve 1-hour sessions of virtual reality featuring two separate treatment catalogues of interactive experiences, games, or videos.

Figure 2: Painting on a Virtual Canvas

CONFIDENTIAL

This material is the property of the NYU School of Medicine and Langone Medical Center. Do not disclose or use except as authorized in writing by the study sponsor

A) The interactive catalogue includes a virtual 3D canvas that participants may paint upon, completion of daily tasks in a virtual kitchen, guided virtual meditation, interaction with music corresponding to the beats per minute of a song, virtual assessment of hand-eye coordination and range of motion among other experiences. See Figure 2 for an illustration of the virtual painting program.

B) The passive VR catalogue includes videos that are non-interactive and passively viewed. Participants may look in 360° at videos that include nature (i.e. underwater biomes, penguins and other animals, earthly biomes), education, and art among others in relaxing or exciting environments.

Participants may receive one of these two catalogues to complete over the course of their participation, regardless of study group assignment.

Each session will be supervised by a study technician trained to troubleshoot any problems related to the VR system, computer, games, or participants' intolerance of VR. All

sessions will be completed at the NYU Ambulatory Care Center.

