7.1 Study Procedures/Evaluations

Participants will complete an informed consent form before any study procedures begin. Participants under the age of 18 will complete an assent form while their legal parent or guardian will complete a consent form.

Participants will complete relevant assessments listed in [Table 2](#) before undergoing a VR session.

Participants may complete as much as one hour of VR therapy during any given session.

Study Group 1: There may be as many as twelve VR sessions during the course of the study. Study personnel will be available to guide participants during the entire duration of the VR session and ensure each session is completed safely. VR treatment will entail use of computer software designed to immerse participants and engage them in exercises. Software includes virtual painting, walking through vivid and calming settings, solving puzzles, among others.

Study Group 2: Similar to study group 1, study personnel will be available to guide participants throughout each VR session. VR treatment will be identical to study group 1.

Participants with MS will only be able to receive eight treatment sessions in this study group and will complete their treatment over four weeks.

Two treatments sessions must be completed each week (of the four weeks) and separated by at least one day. For example, if a participant completes one of their weekly treatments on Monday, they are not able to complete the treatment on Tuesday but may come in on any of the remaining weekdays that study staff are available.

Participants will attend a baseline visit with assessment and training procedures and receive their first treatment immediately after all baseline assessments. Participants will then complete the remaining seven treatment sessions over four weeks. At the final treatment session, participants will repeat assessments. One week following the final treatment session, participants will be asked to return to clinic to complete assessments once more to test cumulative benefits one week following treatment end.

CONFIDENTIAL

This material is the property of the NYU School of Medicine and Langone Medical Center. Do not disclose or use except as authorized in writing by the study sponsor

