12.3.2 Consent Procedures and Documentation

Subjects who are eligible for this study and are over 18 years of age will be asked, following an appropriate discussion of risks and benefits, to give consent to the study for further study procedures. When a minor who was previously enrolled in the study through parental or a guardian's consent and participant assent turns 18 years of age, they will complete a new consent form for adults (they will not require parental or guardian signature as an adult) before the completion of any further study procedures.

Parental Permission: A portion of subjects who are eligible for this study are under 18 years of age, and written permission from parents or legal guardians will be required for participation. After determining that a subject is eligible, the site investigator or designee will approach the parent or legal guardian to offer participation for their child in the study. The parent or legal guardian will be informed about the objectives of the study and the potential risks and benefits of participation. If the parent or legal guardian refuses permission for their child to participate, then all clinical management will be provided by the clinical staff in accordance with institutional practice and judgment.

Child Assent: Children will be asked, following an age-appropriate discussion of risks and benefits, to give assent to the study or further study procedures.

Subject Capacity: All participants will be confirmed to have the capacity to provide consent by a member of the core physician group as described above. Any participants that could minimally meet the criteria for cognitive impairment will not be enrolled into the study.

Debriefing Procedures: No information will be purposely withheld from the subjects. A clinical neuropsychologist (PI) and the treatment team will be available to answer any questions concerning the tests and results that may arise. An enrollment log will be maintained and consent and assent forms will be kept in secure location separate from the participant's data.

After review of the consent or assent form and prior to the start of the first session, the PI or one of the trained study staff members will obtain written consent or assent with a signature of the patient on the consent or assent form. All original signed consent forms will be maintained in the study file, separate from the participant data.

CONFIDENTIAL

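### Group 2 is labelled single-blind to catalogue, but the catalogues differ in whether the user acts or only watches, so participants must know which content they get, and the primary outcome is self-reported.

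*Combined protocol and SAP*

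**What the plan says.** The Methodology row of the Protocol Summary describes Group 2 as "Single blinded, randomized treatment allocation to one of two VR treatment conditions". Section 4.1 says who is blinded and to what: "Participants will be blinded to the VR treatment catalogue they receive".

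Section 6.1.1 describes the two catalogues. Of one: "The interactive catalogue includes a virtual 3D canvas that participants may paint upon, completion of daily tasks in a virtual kitchen", along with guided meditation and interaction with music. Of the other: "The passive VR catalogue includes videos that are non-interactive and passively viewed". On exposure it says: "Participants may receive one of these two catalogues to complete over the course of their participation, regardless of study group assignment".

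Section 7.1 says of Group 2 that "VR treatment will be identical to study group 1", and the Summary labels Group 1 open-label. It also says that "study personnel will be available to guide participants throughout each VR session". Group 2 participants have eight sessions over four weeks.

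The primary outcome is patient-reported. Section 4.2.2 names PROMIS pain intensity and interference; section 9 names PROMIS pain interference from baseline to the study end visit, compared between the two conditions.

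Under Debriefing Procedures, section 12.3.2 says: "No information will be purposely withheld from the subjects".

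**The concern.** The thing said to be masked is the content the participant directly experiences. Someone painting on a virtual canvas knows that they are not passively watching a video, and the reverse holds too. The plan therefore claims a design property that its own description of the treatments rules out.

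This matters because of the outcome. When participants rate their own pain and know what they are receiving, a difference between catalogues in how much benefit they expect can enter the between-group difference alongside any treatment effect. A reader told that the trial was single-blind would give that explanation less weight than it deserves. Section 4.1 presents Group 2 as determining efficacy, so the label bears on how the main result will be read.

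**Working it through.** **1. The passages side by side**

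| Question | What the plan gives | Where |
|---|---|---|
| Who is blinded? | The participant | Summary; 4.1 |
| To what? | The catalogue received | 4.1 |
| How do the catalogues differ? | The user interacts, or only watches | 6.1.1 |
| Does Group 2 treatment differ from open-label Group 1? | No, it is identical | 7.1 |
| Is a masking procedure described? | None found | whole document |
| Are staff or assessors said to be blinded? | No; staff guide the sessions | 7.1 |
| Is an expectancy or blinding check listed? | No instrument is titled as one; the contents of the VR questionnaires are not shown | 7.2, Table 3 |
| Who reports the primary outcome? | The participant | 4.2.2; 9 |

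The first three rows cannot all hold. Blinding to the catalogue requires that the participant cannot tell interactive from passive content, and that difference is what defines the catalogues.

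**2. The plan's own figures**

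The blinding claim carries no figure. The nearest stated figure is the 89% power in section 9. It cannot be reproduced, because the effect size, SD, alpha, sidedness and test are not given, and the point here does not depend on it.

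The number per arm does follow. Section 9 gives n = 44 and dropout of up to 10%: 44 × 0.90 = 39.6, or 19.8 per arm with equal allocation. That agrees with the plan's 20 or more completers per group to within rounding. I use 20.

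**3. Illustration of what a reporting bias would do**

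Assumptions, none of them from the documents: a two-sample t-test at two-sided 5%, no true treatment effect, and a shift of b SD between arms caused only by expectation.

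- Degrees of freedom: 2 × 20 − 2 = 38; critical value t = 2.024.
- Non-centrality: b × √(20/2) = 3.162 b.
- Rejection rate: P(T > 2.024) + P(T < −2.024), with T non-central t on 38 df.

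| Assumed b (SD) | Non-centrality | Significant, either direction | Of which in the biased direction |
|---|---|---|---|
| 0 | 0 | 5.0% | 2.5% |
| 0.2 | 0.632 | 9.5% | 9.0% |
| 0.3 | 0.949 | 15.2% | 15.0% |
| 0.5 | 1.581 | 33.8% | 33.8% |

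The either-direction column is the one to compare with the nominal 5%. At b = 0.2 the ratio is 9.5/5 = 1.9. With 22 per arm (no dropout) the either-direction figures are 9.9%, 16.3% and 36.7%.

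**The case against.** The best defence is that the blinding was meant in a weaker sense: participants know what they are doing in the headset, but not that another catalogue exists, or not which one is expected to do better. This is possible. Section 6.1.1 has each participant receive one catalogue, both catalogues run on the same VR system with the same Group 2 schedule and staff guidance, and nothing in the documents names either as the favoured or the control condition. The consent and assent forms, which would settle what participants are told, are stored separately and are not available here. This stands as a limit on what can be concluded about bias. It does not rescue the text: section 4.1 claims blinding to the catalogue, and the weaker sense is stated nowhere.

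Three stronger readings are tempting, and the documents support none of them.

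- A reader might infer from section 12.3.2 that even masking of the hypothesis is ruled out. The sentence is a general statement under Debriefing Procedures, followed by one about answering questions on tests and results. It does not say that participants are told which catalogue is expected to work. It needs to be made consistent with whatever masking is claimed, but it does not exclude masking.
- A reader might infer that the primary contrast is biased. Knowing the content is not the same as expecting more from it. No direction or amount of differential expectation can be derived from the plan.
- A reader might take the rejection rates above as the trial's false-positive rate. They show what any bias of the assumed size would do in a trial with 20 per arm, not that this trial has one.

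**Conclusion.** The point holds as a conflict between the blinding claim in the Summary and section 4.1 and the treatment description in section 6.1.1. Participants will know the type of content they receive, and the primary outcome is their own report. The between-catalogue contrast should therefore be interpreted as one made without participant blinding to content.

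Confidence is high on the wording conflict, which rests only on the protocol's text. It does not extend to bias: the size of any effect on the result is unknown. The 9.5% to 33.8% range is conditional on assumed shifts of 0.2 to 0.5 SD, a two-sided 5% t-test and 20 completers per arm. Lack of blinding to content is hard to avoid when the treatments are experiences of this kind, and is not in itself the fault. Describing the comparison as blinded is.

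**What to change.** 1. In the Protocol Summary and section 4.1, replace the blinding claim with a statement that Group 2 participants are aware of the content of their catalogue.
2. Claim masking to the study hypothesis, or to the existence or nature of the comparator, only if the sponsor confirms that the consent materials and session procedures achieve it. If so, say how, and make the wording consistent with the no-withholding statement in section 12.3.2.
3. In section 9, state that the between-catalogue comparison will be interpreted as a comparison of self-reported outcomes without participant blinding to content.
4. Optional: if the existing VR questionnaires do not already ask it, add one item on expected benefit after the first exposure and report it descriptively by arm. It should not be used as a covariate to remove bias. Asked before exposure, when the participant has not yet seen the catalogue, it says nothing about expectation specific to that catalogue; asked afterwards, it is a post-randomisation variable, and adjusting for it could remove part of the treatment effect.

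The cost is wording in three places, checking section 12.3.2 against any masking claimed and, if the option is taken, one questionnaire item. Sample size, randomisation and treatment are unchanged. The downside is a less favourable design label.

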4.2 Study Endpoints

4.2.1 Study Group 1 (Neurological Disorders): Study Endpoints

Primary study endpoint will be completion of at least one VR session and change in baseline measures.

Secondary study endpoint will be lack of tolerance of VR protocols. If a participant is unable to complete two full VR sessions due to any possible side effect (i.e. Dizziness or nausea) the session and participant's participation in the study will be terminated (see Assessment of Safety below).

4.2.2 Study Group 2 (Chronic Pain in MS): Study Endpoints

Primary study endpoint will be change in the Patient Reported Outcomes Measurement Information System (PROMIS) pain intensity and interference measures administered at baseline, treatment end, and study end.

Secondary outcomes will include additional measures of pain and other symptoms (i.e. mood and fatigue). We will also measure the acute effects of the treatment on pain before and after each VR session.

5 Study Enrollment and Withdrawal

5.1 Eligibility Criteria for Neurological Disorders

We will include participants who have a confirmed diagnosis of a neurological disorder. Exclusion criteria will include any health condition contraindicated with the use of a VR device (including uncontrolled epilepsy, vertigo, inability to balance, subpar visual and motor skills). See table 1 for full eligibility criteria.

Inclusion Criteria	Exclusion Criteria

• At least 12 years of age• Has been diagnosed by a clinician as having a neurological disorder• Able to commit to the designated period of testing• Able to understand the informed consent process and provide consent to participate in the study• Capacity to complete study procedures as determined by screening personnel• SDMT Z-Score > -3.0• WRAT4 Standard Score > or = 85	
• Visual, auditory, and motor deficits that would prevent full ability to understand study• Visual, auditory, and motor deficits that would prevent full ability to operate VR equipment• Uncontrolled epilepsy• Current diagnosis of vertigo• Uncontrolled mood disorders• History of Psychosis or Schizophrenia

CONFIDENTIAL

This material is the property of the NYU School of Medicine and Langone Medical Center. Do not disclose or use except as authorized in writing by the study sponsor

5.2 Eligibility for MS patients with Chronic Pain

We will include participants who experience pain as a symptom of their MS. Exclusion criteria will include any health condition contraindicated with the use of a VR device (including uncontrolled epilepsy, vertigo, inability to balance, subpar visual and motor skills). See table 2 for full eligibility criteria

Inclusion Criteria	Exclusion Criteria

 • 18-79 years of age • Has been diagnosed by a clinician as having MS • Able to commit to the designated period of testing • Able to understand the informed consent process and provide consent to participate in the study • Capacity to complete study procedures as determined by screening personnel • A Brief Pain Inventory interference score of at least 3 or more. • SDMT Z-Score > -3.0 • WRAT4 Standard Score > or = 85 	
 • Visual, auditory, and motor deficits that would prevent full ability to understand study • Visual, auditory, and motor deficits that would prevent full ability to operate VR equipment • Uncontrolled epilepsy • Current diagnosis of vertigo • Uncontrolled mood disorders • History of Psychosis or Schizophrenia • EDSS Score greater than 6.5 • Unable to tolerate or manipulate VR treatment procedures (as evidenced by VR capability assessment)

5.3 Vulnerable Subjects

Some participants referred may have cognitive impairment or other debilitating symptoms and could be considered a vulnerable population; however, those who lack capacity to consent will not be enrolled in this study. The capacity to consent will be assessed by the study personnel. Since it is not feasible to have an independent party assess every participant that intends to enroll in this especially low risk study, judgement of capacity to consent will be assessed by study staff. The symbol digit modalities test (SDMT) will be used to assess the cognitive status of participants and those who score three standard deviations below their age normative mean (indicating significant cognitive impairment) will be excluded from study. The SDMT can be easily administered in 90 seconds by trained study staff. It will be clearly explained and written for all potential participants that the study is entirely optional and there will be no negative consequences to their decision to not participate.

All child participants will complete a separate assent process in addition to their parent consent. It will be clearly explained and written for all potential participants that the study is entirely optional and there will be no negative consequences to their decision not to participate.

Pregnant women can be enrolled in this study and this study meets the definitions required by the applicable section of 45 CFR Part 46 Subpart B. Specifically, studies have been successfully conducting on nonpregnant women with no additional risk for pregnant women, the risk to the fetus is not greater than minimal and potential new applications to aid pregnant women may be developed through this research, pregnant women who would prefer not to stand, they will have the choice of completing the research protocol seated, and this research does not hold the prospect of direct benefit solely to the fetus and thus the father's consent is not necessary. No inducements, monetary or otherwise, will be offered to terminate the pregnancy. Study staff will have no part in any decisions regarding the timing, method, or procedures used to terminate a pregnancy. This research will play no part in determining the viability of the neonate. Children that are pregnant will not be included in this research.

Neither cognitively impaired people nor prisoners will be enrolled in this study.

CONFIDENTIAL

